17.5 APPENDIX 5: Kings Brief Interstitial Lung Disease Questionnaire

© King's College Hospital 2011

Note: The version of the K-BILD provided in this appendix is for reference only and may differ slightly from the actual versions used on the study. A license to use the K-BILD for the purpose of the study will be obtained prior to study start.

King's Brief ILD Questionnaire (K-BILD)

This questionnaire is designed to assess the impact of your lung disease on various aspects of your life. Read each question carefully and answer by CIRCLING the response that best applies to you. Please answer ALL questions, as honestly as you can.

Protocol No.: ORV-PF-01 Final V4.0 (US) Page 79 of 85

In the last 2 weeks, I have been breathless climbing stairs or walking up an incline or hill.

- 1. Every time
- 2. Most times
- 3. Several Times
- 4. Some times
- Occasionally
- 6. Rarely
- 7. Never

In the last 2 weeks, because of my lung condition, my chest has felt tight.

- 1. All of the time
- 2. Most of the time
- 3. A good bit of the time
- 4. Some of the time
- 5. A little of the time
- 6. Hardly any of the time
- 7. None of the time

3. In the last 2 weeks have you worried about the seriousness of your lung complaint?

- 1. All of the time
- 2. Most of the time
- 3. A good bit of the time
- 4. Some of the time
- 5. A little of the time
- 6. Hardly any of the time
- 7. None of the time

4. In the last 2 weeks have you avoided doing things that make you breathless?

- 1. All of the time
- 2. Most of the time
- 3. A good bit of the time
- 4. Some of the time
- 5. A little of the time
- 6. Hardly any of the time
- 7. None of the time

5. In the last 2 weeks have you felt in control of your lung condition?

- 1. None of the time
- 2. Hardly any of the time
- 3. A little of the time
- 4. Some of the time
- 5. A good bit of the time
- 6. Most of the time
- 7. All of the time

6. In the last 2 weeks, has your lung complaint made you feel fed up or down in the dumps?

- 1. All of the time
- 2. Most of the time
- 3. A good bit of the time
- 4. Some of the time
- 5 A little of the time
- 6. Hardly any of the time
- 7. None of the time

In the last 2 weeks, I have felt the urge to breathe, also known as 'air hunger'.

- 1. All of the time
- 2. Most of the time
- 3. A good bit of the time
- 4. Some of the time
- 5. A little of the time
- 6. Hardly any of the time
- 7. None of the time

8. In the last 2 weeks, my lung condition has made me feel anxious.

- 1. All of the time
- 2. Most of the time
- 3. A good bit of the time
- 4. Some of the time
- 5. A little of the time
- 6. Hardly any of the time
- 7. None of the time

Protocol No.: ORV-PF-01 Final V4.0 (US) Page 80 of 85

9. In the last 2 weeks, how often have you experienced 'wheeze' or whistling sounds from your chest?

- 1. All of the time
- 2. Most of the time
- 3. A good bit of the time
- 4. Some of the time
- 5. A little of the time
- 6. Hardly any of the time
- 7. None of the time

10. In the last two weeks how much of the time have you felt your lung disease is getting worse?

- 1. All of the time
- 2. Most of the time
- 3. A good bit of the time
- 4. Some of the time
- 5. A little of the time
- 6. Hardly any of the time
- 7. None of the time

11. In the last 2 weeks has your lung condition interfered with your job or other daily tasks?

- 1. All of the time
- 2. Most of the time
- 3. A good bit of the time
- 4. Some of the time
- 5. A little of the time
- 6. Hardly any of the time
- 7. None of the time

12. In the last 2 weeks have you expected your lung complaint to get worse?

- 1. All of the time
- 2. Most of the time
- 3. A good bit of the time
- 4. Some of the time
- 5. A little of the time
- 6. Hardly any of the time
- 7. None of the time

13. In the last 2 weeks, how much has your lung condition limited you carrying things, for example, groceries?

Protocol No.: ORV-PF-01

NeRRe Therapeutics Ltd

- 1. All of the time
- 2. Most of the time
- 3. A good bit of the time
- 4. Some of the time
- 5. A little of the time
- 6. Hardly any of the time
- 7. None of the time

14. In the last 2 weeks, has your lung condition made you think more about the end of your life?

- 1. All of the time
- 2. Most of the time
- 3. A good bit of the time
- 4. Some of the time
- 5. A little of the time
- 6. Hardly any of the time
- 7. None of the time

15. Are you financially worse off because of your lung condition?

- 1. A significant amount
- 2. A large amount
- 3. A considerable amount
- 4. A reasonable amount
- 5. A small amount
- 6. Hardly at all
- 7. Not at all

Thank you for completing this questionnaire

King's Brief Interstitial Lung Disease Questionnaire (K-BILD) © King's College Hospital 2011 K-BILD - United Kingdom/English - Mapi.

Protocol No.: ORV-PF-01 Final V4.0 (US) Page 81 of 85

CONFIDENTIAL Protocol No.: ORV-PF-01
NeRRe Therapeutics Ltd

17.6 APPENDIX 6: PROMIS SD SF 8b Sleep Questionnaire

Note: The version of the PROMIS SD SF 8b provided in this appendix is for reference only and may differ slightly from the actual versions used on the study. A license to use the PROMIS SD SF 8b for the purpose of the study will be obtained prior to study start.

PROMIS Item Bank v1.0 - Sleep Disturbance - Short Form 8b

Sleep Disturbance - Short Form 8b

Please respond to each item by marking one box per row.

	In the past 7 days	Not at all	A little bit	Somewhat	Quite a bit	Very much
Slasp108	My sleep was restless	1	2		-	5
Sleep115	I was satisfied with my sleep	5	4	5	-	
Sinep116	My sleep was refreshing	5	~C	3	2	1
814-914	I had difficulty falling asleep	0		3	□	5
	In the past 7 days	\wedge				
		Never	Rarely	Sometimes	Often	Always
8laug87	I had trouble staying asleep	Never 1	Rarely	Sometimes 3	Often 4	Always
Sleep87	6			-		
	I had trouble staying asleep) -	2	3		5
Slavg50	I had trouble staying asleep I had trouble sleeping) - -	2	3	4	5

Protocol No.: ORV-PF-01 16-MAY-2024

³ May 2016 © 2008-2016 PROMIS Health Organization and PROMIS Cooperative Group Page 1 of 1

17.7 APPENDIX 7: Hospital Anxiety and Depression Scale

Note: The version of the HADs provided in this appendix is for reference only and may differ slightly from the actual versions used on the study. A license to use the HADS for the purpose of the study will be obtained prior to study start.

Protocol No.: ORV-PF-01

NeRRe Therapeutics Ltd

Page 83 of 85

Hospital Anxiety and Depression Scale (HADS)

Tick the box beside the reply that is closest to how you have been feeling in the past week.

D	A	Don't take too long over you	D	A	
_		I feel tense or 'wound up':	_	-	I feel as if I am slowed down:
	3	Most of the time	3		Nearly all the time
_	2	A lot of the time	2	-	Very often
_	1	From time to time, occasionally	1		Sometimes
_	0	Not at all	0		Not at all
_	0	Not at an	-		Not at all
		I still enjoy the things I used to enjoy:			I get a sort of frightened feeling like 'butterflies' in the stomach:
)	0.	Definitely as much	7	0	Not at all
1		Not quite so much		1	Occasionally
2		Only a little		2	Quite Often
3		Hardly at all		3	Very Often
				0.00	
		I get a sort of frightened feeling as if something awful is about to happen:			I have lost interest in my appearance:
	3	Very definitely and quite badly	3		Definitely
	2	Yes, but not too badly	2		I don't take as much care as I should
	1	A little, but it doesn't worry me	1	B	I may not take quite as much care
	0	Not at all	0	11	I take just as much care as ever
	1000			D	
		I can laugh and see the funny side of things:	ph.		I feel restless as I have to be on the move:
0		As much as I always could		3	Very much indeed
1		Not quite so much now	B	2	Quite a lot
2		Definitely not so much now	. 4	1	Not very much
3		Not at all		0	Not at all
		Worrying thoughts go through my mind:			I look forward with enjoyment to things:
	3	A great deal of the time	0		As much as I ever did
	2	A lot of the time	1		Rather less than I used to
	1	From time to time, but not too often	2		Definitely less than I used to
	0	Only occasionally	3		Hardly at all
	10	I feel cheerful:			I get sudden feelings of panic:
3		Not at all	1/2	3	Very often indeed
2		Not often		2	Quite often
1	-	Sometimes		1	Not very often
	150	The state of the s		-	
)		Most of the time		0	Not at all
		I can sit at ease and feel relaxed:			I can enjoy a good book or radio or TV program:
	0	Definitely	0	-	Often
	1	Usually	1	5	Sometimes
	2	Not Often	2		Not often
_	3	Not at all	3		Very seldom

Please check you have answered all the questions

Protocol No.: ORV-PF-01 Final V4.0 (US)

HADS copyright © R.P. Snaith and A.S. Zigmond, 1983, 1992, 1994.

Record form items originally published in Acta Psychiatrica Scandinavica 67, 361–70, copyright © Munksgaard International

Publishers Ltd, Copenhagen, 1983.

This edition first published in 1994 by nferNelson Publishing Company Ltd (now GL Assessment Ltd), [name]

GL Assessment Ltd is part of the GL Education Group.

www.gl-assesssment.co.uk

Protocol No.: ORV-PF-01 Final V4.0 (US) Page 84 of 85

Protocol No.: ORV-PF-01 NeRRe Therapeutics Ltd

# LIST OF ABBREVIATIONS

Abbreviation	Description
ACM	Ambulatory Cough Monitor
AE	Adverse Event
AICC	Corrected Akaike's Information Criterion
ANCOVA	Analysis of Covariance
AR(1)	1st Order Autocorrelation
BP	Blood Pressure
eCRF	Electronic Case Report Form
BDRM	Blinded Data Review Meeting
BLLQ	Below Lower Limit of Quantification
CIs	Confidence Intervals
CRO	Contract Research Organization
CS	Compound Symmetry
DLCO	Diffusion Capacity for Carbon Monoxide
DSMB	Data Safety Monitoring Board
ECG	Electrocardiogram
ERS	Exposure-Response Set
FAS	Full Analysis Set
FEV 1	Forced Expiratory Volume in 1 Second
FVC	Forced Vital Capacity
GCP	Good Clinical Practice
GRC	Global Rating of Change
GRS	Global Rating of Status
Н0	Null Hypothesis
H1	Alternative Hypothesis
HADS	Hospital Anxiety and Depression Scale
IB	Investigators Brochure
ICH	International Council for Harmonization
IEC	Independent Ethics Committee
IMP	Investigational Medicinal Product

Abbreviation	Description
IRB	Institutional Review Board
IPF	Idiopathic pulmonary fibrosis
IWRS	Interactive Web Response Services
K-BILD	Kings Brief Interstitial Lung Disease (questionnaire)
LCQ	Leicester Cough Questionnaire
LLOQ	Lower Limit of Quantification
MeDRA	Medical Dictionary for Regulatory Activities
MMRM	Mixed Model for Repeated Measures
NK	Neurokinin
NRS	Numerical Rating Scale
PK	Pharmacokinetic
Pop PK	Population PK
PPS	Per Protocol Set
PRO	Patient Reported Outcome
PROMIS SD F 8b	Patient-Reported Outcomes Measurement Information System Sleep Disturbance Short Form 8b Questionnaire
RUCC	Refractory or Unexplained Chronic Cough
SAE	Serious Adverse Event
SAP	Statistical Analysis Plan
SOC	System, Organ, Class
SOP	Standard Operating Procedure
SP	Substance P
SS	Safety Set
SUSAR	Suspected Unexpected Serious Adverse Reaction
TEAE	Treatment Emergent Adverse Event
TMF	Trial Master File
UN	Unstructured
VAS	Visual Analogue Scale

### 1 PURPOSE

This Statistical Analysis Plan (SAP) describes the planned analysis and reporting for NeRRe Therapeutics Study ORV-PF-01 (IPF COMFORT) and is based on protocol Versions 3.0/3.1, dates 05 April 2023.

The purpose of this SAP is to ensure that the data listings, summary tables and figures which will be produced, and the statistical methodologies that will be used, are complete and appropriate to allow valid conclusions regarding the study objectives.

In the event of future amendments to the protocol, this SAP may need to be modified as necessary to account for changes relevant to the statistical analysis.

### 1.1 RESPONSIBLITIES

will perform the statistical analyses and is responsible for the production and quality control of all derived datasets and tables, figures and listings.

### 2 INTRODUCTION

Orvepitant is a potent and selective inhibitor of the human neurokinin (NK) 1 receptor where it blocks the effects of Substance P (SP), the preferred endogenous ligand of the NK1 receptor. The safety and efficacy of orvepitant has previously been evaluated in more than 900 patients and healthy volunteers, including two studies in patients with chronic cough. A full summary of the pharmacology, pre-clinical safety, pharmacokinetics and clinical safety and efficacy can be found in the current version of the Orvepitant Investigator's Brochure.

Idiopathic pulmonary fibrosis (IPF) is a rare and specific form of chronic, progressive, fibrosing interstitial pneumonia in which fibrosis is limited to the lungs. The prevalence is difficult to determine accurately because of the diagnostic criteria used and the populations examined, but the best estimates put the prevalence in the United States (US) at between approximately 14 per 100,000 using narrow criteria and 43 per 100,000 using broad criteria.

The incidence of IPF increases with older age, with presentation typically consisting of insidious onset of symptoms in the sixth and seventh decades of life. It is more common in men than women and most patients are current or past smokers. A history of gastro-oesophageal reflux is also common. IPF usually assumes a course of relentless physiologic deterioration although in some patients it remains stable for extended periods.

The symptoms of IPF have typically been present for months to years before diagnosis. Breathlessness with exertion and cough are the most common symptoms that lead to diagnosis. Fatigue and anxiety are also common symptoms. Bi-basilar fine inspiratory crackles (so-called Velcro crackles) are the most frequent physical examination finding and digital clubbing is seen in 25 to 50% of patients.

 Protocol version 3.0 (US) is active in the US and version 3.1 is active in the UK and Netherlands. In almost all respects 3.0 and 3.1 are identical save for minor country-specific changes in the UK and Netherlands versions. These differences do not affect the SAP.

Page 8 of 50

-

The ORV-PF-01 study is being undertaken to evaluate the efficacy and safety of orvepitant as a treatment for the chronic cough associated with IPF.

### 2.1 STUDY OBJECTIVES

### 2.1.1 Primary Objective(s)

- To evaluate the effect of orvepitant once daily on cough severity, as perceived by patients, with IPF
- To evaluate the safety of orvepitant once daily in patients with IPF

# 2.1.2 Secondary Objective(s)

- To evaluate the effect of orvepitant once daily on other measures of cough burden and on health-related quality of life in patients with IPF
- To evaluate the effect of orvepitant on other comorbidities in patients with IPF

### 2.1.3 Exploratory Objective(s)

- To evaluate the effect of orvepitant once daily on markers of disease activity in patients with IPF
- To evaluate the relationship between plasma concentrations of orvepitant and efficacy in patients with IPF

### 2.2 STATISTICAL HYPOTHESIS

The statistical hypotheses for the primary efficacy endpoints are as follows:

Null hypothesis (H0): There is no difference in the mean change in mean cough severity NRS scores for the orvepitant treatment group compared to placebo.

H0:  $\mu$  (active) =  $\mu$  (placebo)

Alternative hypothesis (H1): There is a difference in the mean change in mean cough severity NRS scores for the orvepitant treatment group compared to placebo.

H1:  $\mu$  (active)  $\neq \mu$  (placebo)

Each comparison will be carried out at the two-sided 5% level of statistical significance. No adjustment will be made for the multiple orvepitant versus placebo group comparisons in this phase 2 study (two in total: 10 mg versus placebo, 30 mg versus placebo) as each dose cohort is tested independently (versus the corresponding placebo) and each is adequately powered for 90% assuming a two-sided type I error of 0.05, not adjusted for multiple comparisons.

### 2.3 STUDY POPULATION

[figure not shown]
The study will include patients with IPF and troublesome chronic cough in whom the cough is attributed to the IPF.

### 2.4 TRIAL DESCRIPTION

The study will be a multi-center, double-blind, randomised, placebo-controlled 2-period crossover design. Two doses of orvepitant, 10 and 30 mg once daily, will be evaluated.

Subjects will participate in one of two cohorts (Cohort 1 [30 mg] and Cohort 2 [10 mg]). Within each cohort, subjects will be randomised to receive either orvepitant or placebo in the first treatment period (Treatment Period A) followed by the alternate treatment in Treatment Period B. There will be a wash-out period of 3 weeks between the two treatment periods. Subjects will be randomised 1:1 to each of the two treatment orders and 1:1 to each cohort.

Subjects will enter a screening period of up to 28 days to determine eligibility. Eligible subjects will be randomised at the Baseline visit and will participate in two identical 4-week treatment periods with the wash-out period between them. There will be a total of 8 visits including the Screening, Baseline and final Follow-up visits (Table 2 of the protocol).

**Figure 1. Study Schematic** 

### 2.5 STUDY SAMPLE SIZE DETERMINATION

# 2.5.1 Estimated Sample Size

Assuming a common standard deviation of 2.7 for the difference between treatment periods, a sample size of 37 subjects per cohort has 90% power if the difference between treatments on the cough severity NRS is 1.5 points and assuming a two-sided type I error of 0.05, not adjusted for multiple comparisons. To allow for non-evaluable subjects/missing data the withdrawal rate and extent of missing data will be monitored as the trial progresses and the actual sample size will be increased accordingly such that data is available for 37 evaluable subjects.

As there have been no previous studies using NRS for cough severity the standard deviation of 2.7 was obtained based on historical data of the change in cough severity measured using VAS. A 2-week observational study has since been completed in which the standard deviation of the change from baseline in NRS was 1.45 (95% CI: 1.14 - 2.01). Using the upper bound of the 95% CI and applying an inflation factor of 1.3 (derived from the observed increase in standard deviation from week 2 to week 12 in the historical VAS study data) resulted in an estimated standard deviation of 2.6. As this is very similar to, and lower than, the standard deviation originally used in the sample size estimation the estimated sample size required was not updated.

The proposed clinically relevant improvement of 1.5 points in the IPF coughing severity scale is an initial estimate based on the findings from the qualitative interviews with IPF patients conducted during the observational study. The qualitative interviews and psychometric analyses being undertaken as part of the current study will confirm (or else amend) this change for use in future studies.

### 2.5.2 Sample Size Re-Estimation

After 24 subjects have completed Treatment Period B (approximately 12 subjects per cohort), the variance of the cough severity NRS data will be reviewed on a fully blinded basis. Up to a maximum of 20 subjects (approximately 10 per cohort) may be additionally recruited if the emerging cough severity NRS data is found to have greater variance than allowed for in the original sample size estimate. Any possible impact on the type I error due to this blinded sample size reassessment procedure is believed to be negligible.

The Sample Size Re-Estimation Plan is provided in Section 14.2.

### 2.6 TREATMENT ASSIGNMENT AND BLINDING

### 2.6.1 Randomisation

Subjects will be randomised on Day 0 in a 1:1 ratio to either Cohort 1 or Cohort 2, and then within each cohort will be further randomised in a 1:1 ratio to receive either placebo or orvepitant in Treatment Period A. Randomisation will be performed centrally via an IWRS. The central randomisation list will be generated by using SAS 9.4 (SAS Institute Inc., Cary, North Carolina, United States of America) or higher.

Page 11 of 50

<sup>2 VOLCANO-2 (A double blind, randomised, placebo controlled study of the efficacy and safety of three doses of orvepitant in subjects with chronic refractory cough), clinical study report, 09 Apr 2020.

<sup>3 IPF-Obs-01 (An observational study to record cough symptom severity in patients with chronic cough due to idiopathic pulmonary fibrosis), clinical study report, 20 Sep 2021.

<sup>4 The sample size re-estimate has been completed using data from 25 subjects and showed that the variance was not greater than that assumed variance in the original calculation. The required number of evaluable subjects per cohort therefore remains 37.

### 2.6.2 Blinding

The study is fully blinded and patients, site study staff or the study operations team will be unaware of both the cohort (and hence dose) to which a subject is randomised and the order of treatment. Blinding will be maintained until all subjects have completed the study and the database has been locked.

Study investigators will be given access to the IWRS system for the purposes of emergency unblinding. Investigators are permitted to unblind treatment for a subject if it is deemed that knowledge of the subject's treatment will impact a subject's future medical care.

If unblinding occurs accidentally this will be considered a protocol deviation. It must be documented in the subject's medical notes and in the trial master file (TMF), and the Sponsor must be informed.

### 2.6.3 Planned and Actual Treatment

Planned treatment will be the one assigned per the randomisation list.

Actual (received) treatment might be different if the study medication kit(s) actually dispensed does not correspond to the kit(s) allocated by IWRS. Thus, actual treatment groups will be used for patients belonging to the Safety Analysis Set – according to the actual treatment dispensed to the patient. If the information on the kit number is not available at the time of the analysis, the actual treatment will be considered as equal to the planned one.

For the analysis of efficacy in the Full Analysis Set (FAS, study populations are defined in Section 4) the intent to treat principle will be followed and subject data will be assigned to the planned treatment group, regardless of the actual treatment provided.

Any occurrence of incorrectly administered treatment should be recorded as a protocol deviation.

### 2.6.4 Carry Over Effects

A potential limitation of any cross-over study is the occurrence of confounding carry over effects between treatment periods. The wash-out period for this study is 3-weeks which, given that the half-life of orvepitant is approximately 33 hours, is expected to be sufficient for the drug to be fully cleared and for cough symptoms to return to baseline levels.

Period-specific baseline values will be used in the analysis of primary and secondary efficacy endpoints, and safety endpoints, when available, to protect against possible carryover effect. Please refer to Section 5.2.2 for more details.

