5.6 Orvepitant in the Treatment of Cough Hypersensitivity

A cough hypersensitivity syndrome can occur both in patients with and without underlying pulmonary disease [34,35]. In many patients with a chronic cough (defined as a cough of at least 8 weeks' duration) there is either no obvious underlying cause for the cough or it is refractory to treatment of the underlying disease (refractory or unexplained chronic cough, RUCC). It is now well established that patients with RUCC have increased sensitivity of the cough reflex pathway such that they cough in response to what should be an innocuous stimulus, for example singing, talking, perfumes and cold air at all (allotussia) and have increased sensitivity to noxious stimuli (hypertussia) [36]. This has been demonstrated experimentally in many challenge studies with, for example, inhaled capsaicin [37-40].

The frequency of coughing in this group of patients tends to be higher than in other disorders associated with chronic cough [13,40]. RUCC patients commonly report a sensation of an urge to cough which is not relieved by coughing [41] and have a reduced ability to voluntarily inhibit coughing [37]. Collectively, these characteristics indicate a form of sensory neuropathy.

Orvepitant has been evaluated in two Phase 2 studies in patients with RUCC and has shown clear evidence of benefit in these trials. The first study, VOLCANO-1, was an open label pilot study in 13 subjects. After 4 weeks of treatment with orvepitant 30 mg once daily there was a significant reduction from baseline in awake cough frequency (-18.9 coughs/hour, p<0.001) that appeared to be sustained for a further 4 weeks after the end of treatment. After 4 weeks there were also improvements in the cough severity VAS (approximately 28% reduction from baseline, p=0.002) and a small (~8%) but significant improvement in the Cough Quality of Life Questionnaire score.

The second study, VOLCANO-2, was a randomised, double-blind, placebo-controlled dose range finding study. Three hundred and fifteen RUCC patients were randomised to receive placebo or orvepitant 10, 20 or 30 mg once daily for 12 weeks. Orvepitant improved all the patient reported

Protocol No.: ORV-PF-01 Final V4.0 (US) Page 22 of 85

Page 23 of 85

outcomes (PRO) assessed in the study, with the improvements being most evident with the 30 mg dose of orvepitant. These are summarised for each dose at Week 12 in Table 1.

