8.7.5 Wash-out Period

At the end of Treatment Period A subjects will enter a washout period during which they will not take study medication. Subjects will, however, continue to complete the IPF Coughing Severity, additional cough severity, and other symptom scales in the eDiary each day.

The nominal washout period duration will be 21 days although it may be varied by up to ± 3 days to accommodate subject and clinic schedules.

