10.1.5 Global Rating of Change Questionnaire for Cough Severity

The global rating of change questionnaire comprises three questions that subjects will complete at Visits 3, 4, 5, 6, 7 and 8

Subjects will be asked to rate the overall change in severity since starting the study of:

- All coughing
- Coughing first thing in the morning
- Any other coughing

They will select one of 7 responses that range from very much worse through no change to very much better (Appendix 3).

It will be completed during the study visit by the subject directly onto a tablet device except at visits conducted remotely in which the subjects' verbal rating will be transcribed onto the tablet by a member of the site staff.

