11.2 Carry Over Effects

A potential limitation of any cross-over study is the occurrence of confounding carry over effects between treatment periods. The wash-out period for this study is 3-weeks which, given that the half-life of orvepitant is approximately 33 hours, is expected to be sufficient for the drug to be fully cleared and for cough symptoms to return to baseline levels.

Protocol No.: ORV-PF-01 Final V4.0 (US) Page 55 of 85

Period-specific baseline values will be used in the analysis of primary and secondary efficacy endpoints, and safety endpoints, when available, to protect against possible carryover effect.

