### 7 EFFICACY ANALYSES

All efficacy endpoints, including responder rates, will be summarised separately for each cohort with descriptive statistics by cohort and visit as appropriate.

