### 7.1 PRIMARY AND SECONDARY EFFICACY ANALYSIS

Efficacy endpoints will be summarised separately for each cohort by descriptive statistics or counts and percentages for each treatment group at each time point, as appropriate. All statistical hypothesis tests and confidence intervals will be two sided, using a type I error rate of 0.05. No adjustments for multiple comparisons will be used.

The change from baseline of parameters in Week 4 (and Week 2 where also relevant) will be summarised for each treatment group in the FAS population.

Statistical comparisons for the primary and secondary endpoints will be done separately for each cohort as described below in each subsection. For the primary endpoint and secondary endpoints that are a daily numerical or verbal rating scale, an analysis of covariance (ANCOVA) model will be used with the response variable as the change from baseline in the mean score at the timepoint of interest, and predictor variables (fixed effects) as treatment, baseline mean score for the endpoint, period and interaction effect between treatment and period. Subject will be included as a random effect. Investigation of other covariates such as age and sex and their impact on the results may be done post-hoc. Sample SAS code for the ANCOVA is provided below.

Normality of error terms may be checked with QQ plots or other methods. If normality assumptions are considered severely violated, log transformation will be attempted first to see if that fixes the issue. If the normality assumption is still violated after applying transformation, a non-parametric method (e.g., Wilcoxon signed-rank test) will be used for conducting treatment comparison between orvepitant (10 mg or 30 mg once daily) and placebo.

All efficacy data, both patient-reported scores/assessments and derived parameters, will be listed.

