### 7.1.2.8 Patient Global Rating of Change

Patient global ratings of change for all coughing, early morning coughing and rest of the day coughing will be summarised in the same way as the patient global rating of status with frequency tables for each category at weeks 2 and 4. Shift from baseline summaries will be not applicable as there is no baseline recorded for this endpoint.

Additionally, the patient global rating of change analysis will combine the numerical levels into the following groups for each question in the patient global rating analysis:

- Improved Global Rating of Change: Scores 1, 2, 3
- No Change: Score 0

• Worsened: Scores -3, -2, -1

For each question, frequency tables will be provided for each of the combined categories above at weeks 2 and 4.

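### Does the plan need a by-sequence check that cough has returned to baseline after the wash-out?

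*SAP*

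**What the plan says.** Protocol 11.2 and SAP 2.6.4 give the same argument. With a half-life of about 33 hours, the 3-week wash-out "is expected to be sufficient for the drug to be fully cleared and for cough symptoms to return to baseline levels". The further safeguard is that period-specific baselines are "used in the analysis of primary and secondary efficacy endpoints, and safety endpoints, when available, to protect against possible carryover effect". For the primary endpoint, the Period B baseline is the mean diary score over the 7 days ending at Visit 5 (SAP 5.2.2). The primary model in SAP 7.1 regresses change on treatment, that baseline, period and treatment-by-period, with subject as a random effect.

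Data on symptom return are collected. During the wash-out, subjects "continue to complete the IPF Coughing Severity, additional cough severity, and other symptom scales in the eDiary each day" (Protocol 8.7.5). The global rating of change has three "questions that subjects will complete at Visits 3, 4, 5, 6, 7 and 8" (Protocol 10.1.5), so Visit 5 is included.

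On reporting, SAP 7 summarises efficacy "with descriptive statistics by cohort and visit as appropriate", and SAP 7.1 does so "for each treatment group at each time point, as appropriate". The global rating of change gets "frequency tables for each category at weeks 2 and 4" (SAP 7.1.2.8). SAP 7.1 also lists all efficacy data, and SAP 10 summarises plasma concentrations at the end of wash-out.

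**The concern.** The half-life supports clearance of the drug. It does not by itself show that cough has returned to its earlier level. Protocol 5.6 gives some reason to ask: in the open-label pilot study, awake cough frequency showed a reduction "that appeared to be sustained for a further 4 weeks after the end of treatment", which is longer than this wash-out.

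Period-specific baselines sound like a full remedy, but they are not when the baseline enters with a fitted slope below 1. A residual in the Visit 5 baseline is then only partly credited. The estimate can be too large if the residual fades during Period B, or too small if it persists. The sensitivity analyses in SAP 7.1.1.2 deal with protocol deviations and missing diary days. The SAP's prose gives the treatment-by-period term no carryover interpretation. At stake is a modest error in the estimated effect, with no named output telling the reader whether the assumption held.

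**Working it through.** **The plan's own figure.** A paired t-test with difference 1.5, SD 2.7 and two-sided 5% gives 89.98% power at n = 36 and 90.8% at n = 37. This reproduces the 37 per cohort in SAP 2.5.1. The matching planning standard error is 2.7/√37 = 0.44.

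**Clearance.** The last dose is on the evening of the Week 4 visit, so the Visit 5 baseline covers about days 15 to 21 after it. That is 15 × 24/33 = 10.9 to 21 × 24/33 = 15.3 half-lives. Clearance is not in doubt.

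**Shift in the planned estimate.** Let L5 and L7 be the residual improvement in orvepitant-first subjects at Visit 5 and at Week 4 of Period B, and let b be the slope of the Week 4 score on baseline. Only one of the four sequence-by-period cells is affected: placebo in Period B of that sequence. Its baseline-adjusted score moves by b·L5 − L7. Averaged over the two placebo cells, the treatment effect shifts by

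(b·L5 − L7)/2.

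The documents give no value for L5, L7 or b. With b = 0.55 to 0.60 assumed:

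| L5 | Left at Week 4 of Period B | Shift by formula | Simulated estimate (true 1.5) |
|---|---|---|---|
| 0 | – | 0 | 1.48–1.50 |
| 0.375 | none | +0.10 to +0.11 | 1.60–1.62 |
| 0.375 | all | about −0.08 | 1.41–1.43 |
| 0.75 | none | +0.21 to +0.23 | 1.71–1.73 |
| 0.75 | half | +0.02 to +0.04 | 1.51–1.52 |
| 0.75 | all | −0.17 to −0.15 | 1.31–1.35 |

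The simulation used 18 + 19 subjects, the SAP model, and variance settings that give an SD of 2.7 for the period difference in change. Shifts of 0.08 to 0.23 are 0.08/0.44 = 18% to 0.23/0.44 = 52% of the planning standard error. For a wider range, with residuals of 0.5 to 1.5 and slopes of about 0.30 to 0.65, the shift reaches about 0.5 either way. That extreme needs a residual as large as the whole 1.5-point effect three weeks after the last dose.

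**What a by-sequence check could show.** For Visit 5 minus Visit 2, 18 versus 19 subjects, the standard error is SD × √(1/18 + 1/19) = 0.329 × SD, and t(35) = 2.03. The SDs are borrowed from the planning section of the protocol, where they describe other changes.

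| SD | 95% half-width | Chance the interval lies above 0 if L5 = 0.75 |
|---|---|---|
| 1.45 | 0.97 | 33% |
| 2.01 | 1.34 | 20% |
| 2.6 | 1.74 | 13% |

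A residual of 0.75 is therefore missed in 67 to 87% of trials. Centred on zero, the interval would exclude a 1.5-point residual only if the SD were below about 2.2.

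**What a Period A-only analysis could show.** Its simulated standard error is 0.56, against 0.37 for the planned model. If the planned model is the efficient one, the two estimates differ by chance with an SD of about √(0.56² − 0.37²) = 0.42. A shift of about 0.2 is half of that and could not be told from noise.

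**Whether the tables already separate the sequences.** SAP 5.3.2 defines separate analysis visits for the two periods, including the end of wash-out. In a two-period cross-over, the placebo group at a Period B visit is exactly the orvepitant-first sequence. Tables by treatment group and period-specific visit therefore show Visit 5 by sequence at full size. Only if a table pooled the periods would the residual be diluted, to L5/2.

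**The case for a change.** The strongest case for a change is that the stated safeguard is partial, that the direction of any error is unknown, and that the outputs are cheap because the data exist. Naming them before unblinding would avoid a post hoc look. Treatment-by-period does not fill the gap: with a 0.75-point residual it reaches 5% significance in only 4 to 7% of simulated trials. Listings give no estimate or interval. A residual near the full 1.5 points is where a check would be most useful, with 40 to 86% power over the SDs above. Cough frequency and the Hull Airway Reflux Questionnaire have no Period B baseline at all.

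Most of this is factually right: no passage names the comparison, and the protection is incomplete. It still does not amount to a defect. A residual near 1.5 points would also show in the by-visit means, if the periods are kept apart. With the Period A baseline only, the shift becomes −L7/2, so those secondary endpoints can only be understated by a residual benefit. The support for any residual is thin: an open-label study in 13 subjects with refractory or unexplained chronic cough, on awake cough frequency rather than severity, with no placebo arm to separate drug effect from placebo response.

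**Conclusion.** No change to the plan is needed. It is true that return of symptoms to baseline is assumed, and that period-specific baselines with a fitted slope protect only in part. Under assumed residuals of 0.375 to 0.75 points and a slope of 0.55 to 0.60, the error is about 0.08 to 0.23 points on an effect of 1.5, in either direction. It is near zero if about half the residual remains, and there is none under the strict null. Larger assumed residuals give more, but the documents offer only weak support for any residual.

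The extra outputs would leave the wash-out, baselines, primary model and efficacy conclusion as they are, and they are too imprecise to confirm or exclude a residual of the size considered. Whether the by-visit tables keep the periods apart and include Visit 5 is a layout choice for the table specifications that follow the SAP (SAP 13.1), and analysts of a cross-over trial would normally make it. For a Phase 2 first assessment of efficacy, relying on a long wash-out with period-specific baselines is a fair trade-off.
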